Hi [name],	Please let us know how you're feeling by answering the short questionnaire below about your COPD. It should only take you 3 minutes and it will really help us.	Many thanks, [Name] [Practice]
	Please complete this questionnaire: florey.url CAT	
	Thank you for taking part in this study. This is the last text message we'll be sending you as part of the study.	

25 APPENDIX 7 - Full survey questionnaire for (1) asthma and (2) COPD patients, including symptom control, medication adherence and NHS utilisation questions

Complete questionnaire for asthma patients

1.	During thome?	he past 4 weeks, how often did your asthma prevent you from getting as much done at work, school or
	a.	All of time time
	b.	Most of the time
	C.	Some of the time
	d.	A little of the time
	e.	None of the time
2.	During t	he past 4 weeks, how often have you had shortness of breath?
	a.	More than once a day
	b.	Once a day
	C.	3 to 6 times a week
	d.	Once or twice a week
	e.	Not at all
3.	_	he past 4 weeks, how often did your asthma symptoms (wheezing, coughing, shortness of breath, chest s or pain) wake you up at night or earlier than usual in the morning?
	a.	4 of more nights a week
	b.	2 to 3 nights a week
	C.	Once a week
	d.	Once or twice
	e.	Not at all
4.	During t medicat	he past 4 weeks, how often have you used your reliever inhaler (usually the blue inhaler) or nebuliser ion?
	a.	3 or more times per day
	b.	1 or 2 times per day
	C.	2 or 3 times per week
	d.	Once a week or less
	e.	Not at all

Protocol: 22 November 2022, v2.0

5.	How would you rate your asthma control during the past 4 weeks?	
	a.	Not controlled at all
	b.	Poorly controlled
	C.	Somewhat controlled
	d.	Well controlled
	e.	Completely controlled
6.	During the past 2 weeks, how often did you forget to take your preventer inhaler?	
	a.	Always
	b.	Often
	C.	Sometimes
	d.	Rarely
	e.	Never
7.	During the past 2 weeks, how often did you alter the dose of your preventer inhaler?	
	a.	Always
	b.	Often
	C.	Sometimes
	d.	Rarely
	e.	Never
8.	During the past 2 weeks, how often did you stop taking your preventer inhaler for a while?	
	a.	Always
	b.	Often
	C.	Sometimes
	d.	Rarely
	e.	Never
9.	During t	the past 2 weeks, how often did you miss out a dose?
	a.	Always
	b.	Often
	C.	Sometimes

- d. Rarely
- e. Never
- 10. During the past 2 weeks, how often did you take less preventer inhaler than instructed?
 - a. Always
 - b. Often
 - c. Sometimes
 - d. Rarely
 - e. Never
- 11. Roughly how many times have you stayed in hospital in relation to your asthma over the past 3 months, if at all?

Put '0' if you haven't had to stay in hospital at all in relation to your COPD over the past 3 months. If you don't remember the exact number, please just put your best guess.

- a. Free text box
- 12. Roughly how many times have you attended an emergency GP appointment with your own GP or a walk-in centre in relation to your asthma over the past 3 months, if at all?

Put '0' if you haven't had to use this service at all in relation to your asthma over the past 3 months. If you don't remember the exact number, please just put your best guess.

- a. Free text box
- 13. Roughly how many times have you called the NHS 111 helpline in relation to your asthma over the past 3 months, if at all?

Put '0' if you haven't had to use this service at all in relation to your asthma over the past 3 months. If you don't remember the exact number, please just put your best guess.

- a. Free text box
- 14. Roughly how many times have you visited an Urgent Care Centre in relation to your asthma over the past 3 months, if at all?

Put '0' if you haven't had to use this service at all in relation to your asthma over the past 3 months. If you don't remember the exact number, please just put your best guess.

- a. Free text box
- 15. Roughly how many times have you visited Accident & Emergency (A&E) in relation to your asthma over the past 3 months, if at all?

Put '0' if you haven't had to use this service at all in relation to your asthma over the past 3 months. If you don't remember the exact number, please just put your best guess.

a. Free text box

Protocol: 22 November 2022, v2.0

Com	olete	que	stionnaire for COPD patients		
1.	1. How often do you cough?				
		a.	0 - I never cough		
		b.	1		
		C.	2		
		d.	3		
		e.	4		
		f.	5 - I cough all the time		
2.	. Ho	How much phlegm (mucus) do you feel you have on your chest?			
		a.	0 - I have no phlegm (mucus) on my chest at all		
		b.	1		
		C.	2		
		d.	3		
		e.	4		
		f.	5 - My chest is completely full of phlegm (mucus)		
3.	. Ho	ow tig	ht is your chest?		
		a.	0 - My chest does not feel tight at all		
		b.	1		
		C.	2		
		d.	3		
		e.	4		
		f.	5 - My chest feels very tight		
4.	. W	hen d	o you get out of breath?		
		a.	0 - When I walk up a hill or one flight of stairs I am not breathless		
		b.	1		
		C.	2		

Protocol: 22 November 2022, v2.0

	d.	3		
	e.	4		
	f.	5 - When I walk up a hill or flight of stairs I am completely out of breath		
5.	How mu	uch are you limited by your COPD when at home?		
	a.	0 - I am not limited doing any activities at home		
	b.	1		
	C.	2		
	d.	3		
	e.	4		
	f.	5 - I am very limited doing activities at home		
6.	How confident do you feel leaving your home?			
	a.	0 - I am confident leaving my home despite my lung condition		
	b.	1		
	C.	2		
	d.	3		
	e.	4		
	f.	5 - I am not confident leaving my home at all because of my lung condition		
7.	How we	ell do you sleep?		
	a.	0 - I sleep soundly at night		
	b.	1		
	C.	2		
	d.	3		
	e.	4		
	f.	5 - I do not sleep soundly because of my lung condition		
8.	B. How much energy do you have?			
	a.	0 - I have lots of energy		
	b.	1		
	C.	2		

Protocol: 22 November 2022, v2.0

d. 3 e. 4 f. 5 - I have no energy at all 9. During the past 2 weeks, how often did you forget to take your regular inhaler? a. Always b. Often c. Sometimes d. Rarely e. Never 10. During the past 2 weeks, how often did you alter the dose of your regular inhaler? a. Always b. Often c. Sometimes d. Rarely e. Never 11. During the past 2 weeks, how often did you stop taking your regular inhaler for a while? a. Always b. Often c. Sometimes d. Rarely e. Never 12. During the past 2 weeks, how often did you miss out a dose? a. Always b. Often c. Sometimes d. Rarely e. Never

Protocol: 22 November 2022, v2.0

- 13. During the past 2 weeks, how often did you take less regular inhaler than instructed?
 - a. Always
 - b. Often
 - c. Sometimes
 - d. Rarely
 - e. Never
- 14. Roughly how many times have you stayed in hospital in relation to your COPD over the past 3 months, if at all?

Put '0' if you haven't had to stay in hospital at all in relation to your COPD over the past 3 months. If you don't remember the exact number, please just put your best guess.

- a. Free text box
- 15. Roughly how many times have you attended an emergency GP appointment with your own GP or a walk-in centre in relation to your COPD over the past 3 months, if at all?

Put '0' if you haven't had to use this service at all in relation to your asthma over the past 3 months. If you don't remember the exact number, please just put your best guess.

- a. Free text box
- 16. Roughly how many times have you called the NHS 111 helpline in relation to your COPD over the past 3 months, if at all?

Put '0' if you haven't had to use this service at all in relation to your asthma over the past 3 months. If you don't remember the exact number, please just put your best guess.

- a. Free text box
- 17. Roughly how many times have you visited an Urgent Care Centre in relation to your COPD over the past 3 months, if at all?

Put '0' if you haven't had to use this service at all in relation to your asthma over the past 3 months. If you don't remember the exact number, please just put your best guess.

- a. Free text box
- 18. Roughly how many times have you visited Accident & Emergency (A&E) in relation to your COPD over the past 3 months, if at all?

Put '0' if you haven't had to use this service at all in relation to your asthma over the past 3 months. If you don't remember the exact number, please just put your best guess.

a. Free text box

Protocol: 22 November 2022, v2.0

Protocol Title: A randomised controlled trial to evaluate the impact of supportive text messages from GP practices on self-reported symptoms and inhaler adherence in patients with asthma and/or chronic obstructive pulmonary disease (COPD) who have been prescribed a preventer (daily) inhaler (Inhaler Trial)

Protocol no: Accurx-001

COMMERCIAL PARTICIPANT IDENTIFICATION CENTRE AGREEMENT

Between

Accurx Ltd, [name]

"Participating Organisation"

AND

GP Practice as detailed in the "Principal Investigator and Service Agreement for the Protocol" (Inhaler Trial protocol, page 2).

"Participant Identification Centre (PIC)"

Each of which shall be a "Party" and collectively the "Parties"

Whereas

- A. The Sponsor is a technology company involved in the research, development, manufacture and sale of technology for the use in life science;
- B. The Participating Organisation is contracted to act as the Processor of the Sponsor (as Controller) for Personal Data Processed for the purpose of the Clinical Trial;
- C. The Participating Organisation wishes to sub-contract with the PIC to undertake Data Processing for the purpose of identifying potential Clinical Trial Subjects for the Clinical Trial.

It is therefore, agreed that the following terms and conditions shall apply to the conduct of the Data Processing undertaken by the PIC for the purpose of the Clinical Trial (as further defined below):

1. Definitions

- 1.1 In this Agreement, the following words shall have the following meanings:
 - Affiliate

means any business entity that controls, is controlled by or is under the common control with the Sponsor, save where there are contractual arrangements in place to exclude such affiliate. For the purposes of this definition, a business entity shall be deemed to control another business entity if it owns, directly or indirectly, in excess of 50% of the voting interest in such business entity or the power to direct the management of such business entity;

Agent

shall include but is not limited to, any person (including any nurse or other healthcare professional) providing services to the PIC under a contract for services (commonly known as an honorary contract) or otherwise any such person's principal employer in the event that it is not the PIG and/or any contracted third party providing services to a Party under a contract for services or otherwise;

Agreement

means this Agreement comprising its clauses, schedules and any appendices attached to it;

Clinical Trial

means the investigation to be conducted at the Site in accordance with the Protocol;

Clinical Trial Subject

means a person enrolled to participate in the Clinical Trial according to criteria detailed in the Protocol;

Controller

shall have the meaning set out in the Data Protection Laws and Guidance;

Data Protection Laws and Guidance

means the GDPR, the Data Protection Act 2018, the Privacy and Electronic Communications (EC Directive) Regulations 2003, as well as any legally enforceable NHS requirements, Codes of Practice or Guidance issued by the Information Commissioner's Office, in each case in force from time to time in England, Northern Ireland, Scotland and/or Wales; and, pending a favourable decision from the competent authorities of the EU on the adequacy of the UK data protection regime will include the requirements set out or referenced in Part Three, Title VII, Article 71(1) of the Withdrawal Agreement signed by the UK and the EU in December 2019;

Data Subject

shall have the meaning set out in the Data Protection Laws and Guidance;

EEA

means the European Economic Area comprising the countries of the European Union as well as Iceland, Liechtenstein and Norway;

GDPR

means Regulation (EU) 2016/679 of the European Parliament and of the Council of 27 April 2016 on the protection of natural persons with regard to the processing of personal data and on the free movement of such data, as it forms part of the law of England and Wales, Scotland and Northern Ireland by virtue of Section 3 of the European Union (Withdrawal) Act 2018 and as amended by the Data Protection, Privacy and Electronic Communications (Amendments etc) (EU Exit) Regulations 2019;

Personal Data

means any and all information, data and material of any nature received or obtained by any Party in connection with this Agreement which is personal data as defined in the Data Protection Laws and Guidance and which relates to a Clinical Trial Subject (or potential Clinical Trial Subject) and/or their treatment or medical history;

Personal Data Breach

means a breach of security leading to the accidental or unlawful destruction, loss, alteration, unauthorised disclosure of, or access to personal data transmitted or otherwise processed;

Personnel

means the persons who will undertake the activities specified at Clause 2.5 on behalf of the PIC;

Participant Identification Centre (PIC)

means the organisation named on page one of this Agreement, being an organisation sub-contracted by the Participating Organisation to Process Personal Data on behalf of the Sponsor to identify potential Clinical Trial Subjects for the Clinical Trial;

Process

shall have the meaning set out in the Data Protection Laws and Guidance (and "process" and "processed" shall be construed accordingly);

Processor

shall have the meaning set out in the Data Protection Laws and Guidance;

Protocol

means the full description of the Clinical Trial with the reference number set out on the front page of this Agreement and incorporated into this Agreement by reference;

Pseudonymised Data

means individual-level data relating to a natural person (as opposed to aggregated data) who is made no longer identified or identifiable from that data by virtue of the replacement of personal identifiers with a code, or equivalent, and which is safeguarded as non-identifiable in accordance with this agreement;

Site

means the physical location(s) where the Clinical Trial will be conducted within the Participating Organisation;

Sub-Processor

means the PIC contracted by the Participating Organisation to Process Personal Data on behalf of the Sponsor (as per GDPR Article 28 (2)).

2. General

- 2.1 Any reference to a statutory provision, code or guidance shall be deemed to include reference to any subsequent modification or re-enactment of it.
- 2.2 The headings to clauses are inserted for convenience only and shall not affect the interpretation or construction of this Agreement.
- 2.3 Where appropriate, words denoting the singular shall include the plural and vice versa and words denoting any gender shall include all genders.
- 2.4 A reference to this Agreement or to any other agreement or document referred to in this Agreement is a reference to this Agreement or such other agreement or document as amended, varied or novated (in each case other than in breach of the provisions of this Agreement) from time to time.
- 2.5 The PIC will Process Personal Data to identify potential Clinical Trial Subjects as follows:
 - 2.5.1 The PIC will forward an invite via the Accurx Batch Messaging Feature for potential Participants meeting the following criteria:

Inclusion criteria:

Participants eligible for enrollment in the study must meet all the following criteria:

- Willing and able to provide informed consent and to comply with the study instructions
- 2. Male and females age 18 or older

- Confirmed diagnosis of asthma and/or COPD as recorded in the patient's GP medical record
- 4. Currently prescribed a preventer inhaler
- 5. Access to a mobile phone
- 6. Ability to check text messages on phone
- 7. Ability to read

Exclusion criteria:

- 1. Inability to understand the study procedures
- 2. Inability or reluctance to provide responses to the study questionnaires
- 3. Inability to receive and respond to text messages
- 2.5.2 The PIC will be provided with the following information to provide to potential participants:
 - a. Study invitation
- 2.6 Where the PIC is constituted in England then this Agreement shall be governed and construed in accordance with the laws of England and Wales and the Courts of England and Wales shall have exclusive jurisdiction to hear any dispute relating to this Agreement.

Where the PIC is constituted in Wales then this Agreement shall be governed and construed in accordance with the laws of England and Wales as applied in Wales and the Courts of England and Wales shall have exclusive jurisdiction to hear any dispute relating to this Agreement.

Where the PIC is constituted in Scotland, this Agreement shall be governed and construed in accordance with the laws of Scotland and the Courts of Scotland shall have exclusive jurisdiction to hear any dispute relating to this Agreement.

Where the PIC is constituted in Northern Ireland, then this Agreement shall be governed and construed in accordance with the laws of Northern Ireland and the Courts of Northern Ireland shall have exclusive jurisdiction to hear any dispute relating to this Agreement.

- 3. Confidentiality and Data Protection Data Protection
- 3.1 The Parties agree:

3.1.1 To comply with all Data Protection Laws and Guidance in processing the Personal Data of Clinical Trial Subjects. This Clause 3 is in addition to and does not replace, relieve or remove a Party's obligations or rights under the Data Protection Laws and Guidance.

3.1.2 When one Party is Processing Personal Data, as Controller, for which the other Party is at that time a separate and independent Controller, to promptly and without undue delay, notify and inform that other Party in the event of any Personal Data Breach that relates to that Personal Data.

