4 OBJECTIVES AND OUTCOME MEASURES

4.1 Primary objective and measurement

Objective	Measurement
The primary objective of the trial is to assess the difference in adherence of self-reported	Changes in the MARS-5 Questionnaire from baseline to 13 and 26 weeks will be measured
medication taking as measured by the MARS-5 Questionnaire	in the intervention and control group

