Supportive text messages (intervention group only)		Х	Х	Х	Х	Х	
MARS-5 Questionnaire		Х		Х		Х	
Asthma Control Test (asthma patients only)		Х		Х		Х	
COPD Assessment Test (COPD pts and pts with both asthma and COPD		Х		Х		Х	
Inhaler prescription frequency assessment		Х		Х		Х	
Emergency admissions assessment		Х		Х		Х	
NHS utilisation assessment		Х		Х		Х	
End of study notification (control group)						Х	
End of study notification (intervention group)							Х
End of study feedback survey (intervention group only)							Х

Protocol: 22 November 2022, v2.0

21 APPENDIX 3 - Intervention group: text message schedule

Week	1							2								3							4						
Day	1	2	3	4	5	6	7	1	2	3	4	5	6	7	1	2	3	4	5	6	7	1	2	3	4	5	6	7	
Message	~		~							~						~			~					~					
Week	5						6							7							8								
Day	1	2	3	4	5	6	7	1	2	3	4	5	6	7	1	2	3	4	5	6	7	1	2	3	4	5	6	7	
Message	>			'					~						>			1					>						
Week	9								10							11							12						
Day	1	2	3	4	5	6	7	1	2	3	4	5	6	7	1	2	3	4	5	6	7	1	2	3	4	5	6	7	
Message		~						~									~									/			
Week				13							14							15							16				
Day	1	2	3	4	5	6	7	1	2	3	4	5	6	7	1	2	3	4	5	6	7	1	2	3	4	5	6	7	
Message	>																~												
Week				17							18							19							20				
Day	1	2	3	4	5	6	7	1	2	3	4	5	6	7	1	2	3	4	5	6	7	1	2	3	4	5	6	7	
Message		~																	~										
Week				21							22							23							24				
Day	1	2	3	4	5	6	7	1	2	3	4	5	6	7	1	2	3	4	5	6	7	1	2	3	4	5	6	7	
Message			~												~														
Week				25							26							27							28				
Day	1	2	3	4	5	6	7	1	2	3	4	5	6	7	1	2	3	4	5	6	7	1	2	3	4	5	6	7	
Message	>											>										~							

Protocol: 22 November 2022, v2.0

22 APPENDIX 4 - Intervention group: text message content

Asthma	- intervention group	
Hi [name],	Thanks for signing up to take part in the study about your asthma. You'll receive your first message from us in the next few days.	Thanks, [Name] [Practice]
	A copy of the information sheet is here: [INSERT LINK TO PDF]. You can come back to this at any point.	
	Remember that if you want to opt out at any time during the next 6 months you can do so via this link: https://forms.gle/N7jGrLjQeAeKQ9ee9	
Hi [name],	Please take 2 minutes to fill out the questionnaire below. This will help us to understand your asthma symptoms and how you're currently using your preventer inhaler. If you do not complete this survey, you will not be able to take part in the study.	Many thanks, [Name] [Practice]

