Hi [name],	Last week we suggested you try and incorporate taking your preventer inhaler into your daily routine. Today take a moment to reflect on how that is going. Have you remembered to take your inhaler more this week now that it is part of a routine?	[Name] [Practice]
Hi [name],	Remember to pick up a new prescription before your preventer inhaler runs out. If you haven't already, you can arrange repeat prescriptions directly with the practice or through your local pharmacy to make things easier.	Thanks, [Name] [Practice]
Hi [name],	Are you finding these messages useful? Let us know by answering two quick questions via the link below. Please complete this questionnaire: [GOOGLE FORM] If you no longer want to receive the messages, you can opt out at [link to opt out].	Many thanks, [Name] [Practice]
Hi [name],	You can reduce the risk of symptoms like wheezing, breathlessness and a tight chest by using your preventer inhaler every day.	[Name] [Practice]
	Please use your inhaler today if you haven't already.	
Good morning [name],	Have you taken your preventer inhaler yet today? Please remember to take it if you haven't already.	Thanks, [Name] [Practice]
Hi [name],	Asthma flare ups can have a negative impact on your day-to-day life. Using your preventer inhaler today - and every day - lets you gain greater control of your symptoms to help avoid these flare-ups.	[Name] [Practice]
	If you haven't already, please use your inhaler today.	
Hi [name],	Some people tell us that they mean to use their inhaler every day but simply forget. If you struggle with this too, try keeping it somewhere where you'll see it every day, such as by your toothbrush, next to the kettle, or on your bedside table.	Thanks, [Name] [Practice]
Hi [name],	Hopefully you're finding that your asthma is better controlled now that you've been taking your preventer inhaler regularly. We know that many patients find it difficult to remember to take their preventer inhaler when their symptoms improve, but please try to keep taking it as prescribed to help stop your symptoms getting worse and reduce the risk of a flare-up.	Thanks, [Name] [Practice]
Hi [name],	We've been sending you these messages for 3 months now, and we hope that you're finding them helpful. Please answer the short questionnaire below about your asthma to help us understand your symptoms and how you're using your preventer inhaler. Please complete this questionnaire: florey.url ACT/CAT	Many thanks, [Name] [Practice]

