Good morning [name],	Make sure your asthma is well-controlled by using your preventer inhaler today - and every day. Remember that if you no longer want to receive the messages, you can opt out at [link to opt out].	Thanks, [Name] [Practice]

Hi [name],	Remember that you need to take your preventer inhaler every day. Taking your inhaler every day will reduce your risk of experiencing asthma symptoms and help build up protection in your airways over time.	Thanks, [Name] [Practice]
Hi [name],	Your preventer inhaler is designed to prevent asthma symptoms. It's important to use it every day, as prescribed, and not only when you experience asthma symptoms.	[Name] [Practice]
	Please try to take it even when your asthma doesn't feel particularly bad.	
Hi [name],	Please remember to take your inhaler today if you haven't taken it yet. By taking your preventer inhaler today - and every day - you are helping to keep your asthma under control.	Thanks, [Name] [Practice]
Good morning [name],	Don't forget to pick up a new prescription before your preventer inhaler runs out. If you haven't already, you can arrange repeat prescriptions with your local pharmacy to make things easier.	Thanks, [Name] [Practice]
Good morning [name],	Just a quick reminder to take your inhaler today if you haven't already. Using your inhaler regularly helps us keep your asthma under control.	Thanks, [Name] [Practice]
Hi [name],	You've now received these messages for the past 6 months. Please let us know how you're feeling by answering the short questionnaire below about your asthma. It should only take you 3 minutes and it will really help us to understand whether these reminders benefit patients.	Many thanks, [Name] [Practice]
	Please complete this questionnaire: florey.url ACT/CAT	
Hi [name],	Final step! Tell us how you found receiving messages from us at Accurx on behalf of your GP practice over the last 6 months. Please could you take 2 minutes to share your feedback through the anonymous survey link below? The deadline for completing the survey is [date].	Thanks, [name] accuRx
	[survey link]	
	Thank you for taking part in this study. This is the last text message we'll be sending you as part of the study.	

COPD - i	COPD - intervention group							
Hi [name],	Thanks for signing up to take part in the study about your breathing condition - COPD. You'll receive your first message from us in the next few days.							

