	Any messages we send you over the next 6 months will relate to your preventer inhaler (the one that is prescribed to be taken every day) NOT a reliever or rescue inhaler (one only prescribed to take as and when you need to). If you're unsure which inhaler is which, please get in touch with your local pharmacy or the practice.					
Hi [name],	Please answer the short questionnaire below about your asthma to help us understand your symptoms and how you're using your preventer inhaler. Please complete this questionnaire: florey.url ACT/CAT	Many thanks, [Name] [Practice]				
	Please complete this questionhaire, horey,un ACT/CAT					
Hi [name],	Please let us know how you're feeling by answering the short questionnaire below about your asthma. It should only take you 3 minutes and it will really help us.	Many thanks, [Name] [Practice]				
	Please complete this questionnaire: florey.url ACT/CAT					
	Thank you for taking part in this study. This is the last text message we'll be sending you as part of the study.					

COPD - control group									
Hi [name],	COPD. You'll receive your first message from us in the next few days.	Thanks, [Name] [Practice]							
	A copy of the information sheet is here: [INSERT LINK TO PDF]. You can come back to this at any point.								
	Remember that if you want to opt out at any time during the next 6 months you can do so via this link: https://forms.gle/N7jGrLjQeAeKQ9ee9								

Protocol: 22 November 2022, v2.0

Hi [name],	Please take 2 minutes to fill out the questionnaire below. This will help us to understand your COPD symptoms and how you're currently using your regular inhaler. If you do not complete this survey, you will not be able to take part in the study.	Many thanks, [Name] [Practice]
	Please complete this questionnaire: URL [COPD CAT Questionnaire]	
	Any messages we send you over the next 6 months will relate to your regular inhaler (the one that is prescribed to be taken every day) NOT a reliever or rescue inhaler (one only prescribed to take as and when you need to). If you're unsure which inhaler is which, please get in touch with your local pharmacy or the practice.	
Hi [name],	Please answer the short questionnaire below about your COPD to help us understand your symptoms and how you're using your regular inhaler. Please complete this questionnaire: florey.url CAT	Many thanks, [Name] [Practice]

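### The follow-up survey invitations differ by arm after randomisation, an avoidable asymmetry in how the self-reported primary outcome is measured

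*Protocol*

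**What the plan says.** Protocol section 4.1 defines the primary measurement: "Changes in the MARS-5 Questionnaire from baseline to 13 and 26 weeks will be measured". Section 10.1 says one survey carries MARS-5, the ACT or CAT, and the questions on NHS use and admissions. Appendices 4 and 6 give the texts that deliver that survey to each arm, all signed in the practice's name.

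- **Baseline.** Both arms get the same request. For asthma it begins "Please take 2 minutes to fill out the questionnaire below. This will help us to understand your asthma symptoms".
- **Week 13, intervention.** The text opens "We've been sending you these messages for 3 months now, and we hope that you're finding them helpful", for asthma and COPD alike, and then makes the survey request.
- **Week 13, control.** Only the request is sent. For asthma it is "Please answer the short questionnaire below about your asthma to help us understand your symptoms and how you're using your preventer inhaler".
- **Week 26, intervention.** The text opens "You've now received these messages for the past 6 months", asks how the patient is feeling, and says of answering that "it will really help us to understand whether these reminders benefit patients". The COPD text does the same.
- **Week 26, control.** The request says "It should only take you 3 minutes and it will really help us" and gives no further purpose. The text then announces that it is the last one of the study.

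Section 7.5 and Appendix 2 provide a separate anonymous feedback survey at week 28, for the intervention arm only.

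**The concern.** The survey invitation is part of the measurement, not of the treatment, since both arms receive it. From week 13 on, it reminds one arm of the messages in the same text that opens the questionnaire. At week 26 it also tells that arm that the answers bear on whether the reminders work. Respondents know whether they have been getting messages, and MARS-5 asks how often they forgot, altered, stopped or skipped doses, so a cue of this kind can move answers without any change in inhaler use.

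Two effects are possible. One is a shift in what intervention patients report. The other is a difference in who replies. The second matters because section 10.1 limits the survey dataset to people who completed baseline and at least one follow-up survey. The ACT, CAT, hospital stays and NHS use come through the same survey, so they are exposed too. Among the listed outcomes, only the prescription-request interval comes from records.

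**Working it through.** **Step 1: compare the texts.**

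| Occasion | Shared by both arms | Intervention only | Control only |
|---|---|---|---|
| Baseline | whole survey request | nothing | nothing |
| Week 13 | survey request | reference to 3 months of messages and hope that they help | nothing |
| Week 26 | request to say how the patient feels; 3-minute estimate | reference to 6 months of messages; purpose is to learn whether reminders benefit patients | last-message line |

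The pattern holds for asthma and for COPD. Because the texts differ only after baseline, and differ exactly by arm, the cue is fully confounded with allocation. The ANCOVA in section 10.1 adjusts for differences at baseline and so cannot separate the cue from a treatment effect.

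**Step 2: the plan's own figure.** Section 10.1 gives 400 COPD patients per arm for 80% power on the CAT. It states neither a difference nor an SD, so this cannot be reproduced directly. With an assumed standardised difference of 0.20, n = 2 × (1.960 + 0.842)² / 0.20² ≈ 392.5, or 393 per arm, which is consistent with 400. It concerns the CAT and says nothing about MARS-5. The point does not depend on it.

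**Step 3: what a small shift would do.** Inputs:

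- About 4,000 at baseline, 1:1 (sections 10.2 and 7.4): about 2,000 per arm.
- Rejection when the 95% interval excludes zero (section 10.1): two-sided 5%, so 2.5% in favour of the intervention.
- Responders per arm for MARS-5: not stated. Assumed 1,000 to 1,600, which is 50% to 80% of 2,000.
- Reporting shift b caused by the wording: not stated. Assumed 0.05 and 0.10, in units of the SD used in the comparison.
- True effect: zero.

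Formula: P(false benefit) = 1 − Φ(1.96 − b / √(2/n)).

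| n per arm | √(2/n) | b = 0 | b = 0.05 | b = 0.10 |
|---|---|---|---|---|
| 1,000 | 0.0447 | 2.5% | 1 − Φ(0.842) = 20.0% | 1 − Φ(−0.276) = 60.9% |
| 1,600 | 0.0354 | 2.5% | 1 − Φ(0.546) = 29.3% | 1 − Φ(−0.868) = 80.7% |

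At the protocol's 400 per arm for the CAT, the same formula gives 10.5% and 29.3%. If all 2,000 per arm replied, it gives 35.2% and 88.5%.

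The difference detectable with 80% power is 2.802 × √(2/n): 0.125 SD at 1,000 per arm and 0.099 SD at 1,600. A trial of this size can therefore declare significant a difference small enough to arise from reporting alone.

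**The case against.** The strongest reply has five parts.

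**The two follow-up texts are not equally leading.** A reader might infer that both tell patients their answers judge the reminders. They do not. That statement is in the week 26 text only; week 13 carries the milder hope. This stands.

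**Direction is not shown.** The week 26 sentence asks whether the reminders help, which is formally two-sided, and the request concerns how the patient feels, not inhaler use. The cue may therefore bear on the ACT and CAT at least as much as on MARS-5, and selective response could act either way. It is tempting to say that MARS-5 is biased towards benefit. The documents support only that it may be, with benefit the more plausible direction.

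**Controls may also know the hypothesis.** The study's short title refers to support by text message, and all participants can open an information sheet that is not available here. So it cannot be said that only one arm was told the aim. What is one-sided is the reminder at the moment of measurement.

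**The arithmetic is generic.** It would apply to any unblinded self-report, and the intervention arm also gets months of texts urging inhaler use, including one just before the week 13 survey that presumes better use. The extra effect of the survey wording is unknown. This stands, and limits the figures to illustration.

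**Checks exist.** Prescription-request intervals are record-based, and section 8.3 counts clicks on the questionnaire links. Both help to detect a problem. Neither corrects a biased MARS-5 difference.

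None of this gives a reason to word the invitation differently by arm.

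**Conclusion.** The point holds as an avoidable measurement asymmetry. The invitations match at baseline and differ by arm at both follow-up times of the primary outcome, for both conditions. This may bias reported adherence and symptoms and may alter response, and no analysis can undo it.

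The 20-29% and 61-81% figures show how sensitive the trial would be to shifts of 0.05 and 0.10 SD with 1,000 to 1,600 responders per arm. They are not estimates of this trial's false-positive rate, because the shift and the responder numbers are both assumptions. Nor should a reader conclude that identical texts would bring the error rate back to 2.5%. That would hold only if no other reporting bias existed, and intervention patients would still know that they had been receiving messages. The change removes only the part due to the wording of the request.

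**What to change.** Use one identical, neutral survey invitation per condition in both arms at weeks 13 and 26.

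- **Week 13:** send the existing control text to both arms.
- **Week 26:** send the control text to both arms without its closing line about the last study message. That line would be untrue for the intervention arm, which is contacted again at week 28. Give it to controls in the week 26 end-of-study notification that Appendix 2 already lists. Appendix 5 marks only one control text that week, so check whether the notification needs its own entry.
- **Messages and their benefit:** remove every reference from the intervention-arm survey invitations and keep such questions for the week 28 feedback survey.

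Cost: six templates are edited, four for the intervention arm (two conditions × two time points) and two for the control arm at week 26. The change goes to the ethics committee, with approval under section 15.3 if it is classed as substantial. Sample size, survey timing and analysis are unchanged.
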